5.3. Assessment of Subject Compliance

The study coordinator will assess the subject's compliance with the protocol by counting the pills remaining in the prescription obtained for the study. The date the prescription was filled relative to the study visit date will also be noted.

5.4. Data & Specimen Banking for Future Research Use

This will not be done.

5.5. Genetic/Genomic Research Activities

No genetic/genomic research activities are planned.

5.6. Costs to the Subject

Subjects will be prescribed Pioglitazone, a drug that costs \$12 per month. The cost of drug will be paid by the Department of Dermatology. Costs of blood tests specifically related to the study to monitor safety of drug administration are also covered by the department. The costs related to subject's cancer treatment (standard care) will be charged to insurance as is routine. There is only Department of Dermatology clinical grant support for this project for coverage of medication costs.

5.7. Payment for Participation

There is no payment for participation.

5.8. Return of Individual Research Results

Any side effects suspected to be related to the study drug will be reported to the subject at the time of their detection. Subjects who have significant side effects attributable to study drug will be dropped from the study, and the side effects reported to their physician. Since the study is not blinded, subjects will be directly aware of whether there is a detectable difference in the incidence of their skin cancers.

6. CONCOMITANT AND DISALLOWED MEDICATIONS

Subjects will be asked to continue their usual medications. Potential subjects with type 1 or type 2 diabetes will not be enrolled.

7. SUBJECT WITHDRAWALS

Subjects will be advised in the written informed consent provided that they have the right to withdraw from the study at any time without prejudice, as well as being notified of this by the study coordinator. Subjects may be withdrawn by the investigator without their consent for non-compliance, intercurrent illness, or pregnancy (Pioglitazone is pregnancy category C) for suspected drug related side effects. Stop criteria to be used are clinical or laboratory assessments revealing grade II abnormalities as defined by Common terminology Criteria for adverse event V.3. No additional study activities will be completed by the subject prior to withdrawal from the

study. Subjects withdrawn from the study will be replaced.

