5.2. Safety Assessments

The main safety issue associated with this trial is whether an adverse effect will occur in patients due to the administration of pioglitazone. Clinical endpoints to monitor for safety are: weight, pedal edema, dyspnea, heart failure, headache, myalgia, fracture, liver injury and vision changes related to macular edema, blood in the urine or other changes that are out of the ordinary. The study related blood monitoring is to ensure there are no preexisting conditions that make participants susceptible to drug-related side effects. For instance, individuals with preexisting liver disease may have hepatotoxicity when taking pioglitazone, hence they must be excluded from participation. However, since participants could develop new diseases while participating, blood will also be taken from subjects taking pioglitazone to screen for such concerns. At a study visit approximately 60 days after drug initiation, blood work will be repeated to detect changes suggesting drug related side effects. Monitoring of blood for glucose levels, altered liver function, or decreased Hemoglobin could indicate the patient should stop taking the study drug. Tests to be followed will be CBC and CMP at baseline, approximately 60 days after starting drug and at the end of treatment. Blood test results will be interpreted in the context of the clinical exam. The patient population being studied has co-morbidities that require them to regularly give blood to monitor their health as part of their routine care, so study related blood draws may not be necessary if these tests are obtained by their providers at appropriate intervals; it will not be necessary to repeat them. The risk of bladder cancer will be monitored by urinalysis. Taking Pioglitazone for > 1 year increases the risk of bladder cancer from 7 in 10,000 to 10 in 10,000. Female patients of child bearing age will have urine pregnancy testing at baseline and at subsequent study visits. **Stop Criteria:** Subjects will be

dropped from the protocol if clinical or laboratory assessment reveals grade II abnormalities as defined by Common terminology Criteria for adverse events V.3. Subjects will also be dropped from the protocol if they are unable to tolerate 30 mg Pioglitazone treatment when the dosage is increased to 30 mg daily after the initial 2 week treatment with 15 mg daily.

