8.5. Subject Withdrawal of Study Drug

If study subjects stop drug treatment (other than as indicated in the protocol) they will be dropped from the study. Compliance will be considered taking the drug appropriately >80% of the time.

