9.2. Serious Adverse Event

A serious adverse event is defined as any adverse medical experience that results in any of the following outcomes:

- death;
- is life-threatening;
- requires inpatient hospitalization or prolongation of existing hospitalization;
- results in persistent or significant disability/incapacity;
- is a congenital anomaly/birth defect; or
- requires medical or surgical intervention to prevent permanent impairment or damage.

9.3. CBC, CMP will be monitored at baseline and at the study visit occurring 60 days after Drug treatment begins. Urinalysis will be checked for Blood at each study visit.

At each subject visit the study staff will assess adverse events by recording all voluntary complaints of the subject and by assessment of clinical and laboratory features. At each study visit, the subject will be questioned directly regarding the occurrence of any adverse experience since his/her last visit.

All adverse events, whether observed by the Investigator, elicited from or volunteered by the subject, will be documented. Each adverse event will include a brief description of the experience, the date of onset, the date of resolution, the duration and type of experience, the severity, the relationship to taking Pioglitazone, contributing factors, and any action taken with respect to Pioglitazone.

Recording of adverse events will occur during the time that the patient is on study drug and for the next study visit after finishing drug. Follow up of adverse experiences will be until the event is resolved or stabilized or for 6 months.

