9.4. Responsibilities for Reporting Serious Adverse Events

The Investigator will record all serious adverse experiences that occur during the study period in the appropriate source documents and/or AE log as applicable. The study period for reporting serious adverse events will be from the time of signing consent to final study visit.

As sponsor of the relevant IND, the PI is responsible for compliance with the FDCA (21 USC §§ 301 e. seq.) as well as the implementing regulations [Title 21 of the CRF]. These responsibilities include reporting any unexpected fatal or life-threatening suspected adverse reactions to the FDA/CDER no later than 7 calendar days after initial receipt of the information.

Additionally, the PI will comply with all federal regulations and RSRB policies regarding the reporting of adverse events.

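### Section 7 rules out an exit assessment for withdrawn subjects, conflicting with the end-of-treatment bloods in 5.2 and the post-drug adverse event recording in 9.3, and follow-up after withdrawal is left undefined

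*Combined protocol and SAP*

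**What the plan says.** **Who is withdrawn.** Section 7 states "Stop criteria to be used are clinical or laboratory assessments revealing grade II abnormalities", graded by CTCAE version 3. Section 5.2 says such subjects are "dropped from the protocol if clinical or laboratory assessment reveals grade II abnormalities". Sections 5.2 and 8.2 also drop subjects who cannot tolerate the 30 mg dose. Section 8.5 adds: "If study subjects stop drug treatment (other than as indicated in the protocol) they will be dropped from the study". Section 7 lets the investigator withdraw a subject for pregnancy, intercurrent illness or non-compliance as well. In each case the subject leaves the study, not only the drug.

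**What happens on leaving.** Section 7: "No additional study activities will be completed by the subject prior to withdrawal" from the study. Withdrawn subjects are then replaced.

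**What other sections require.**
- Section 5.2 lists "CBC and CMP at baseline, approximately 60 days after starting drug and at the end of treatment".
- Section 9.3 has adverse events recorded during drug treatment and at the first study visit once drug has ended. It adds: "Follow up of adverse experiences will be until the event is resolved or stabilized or for 6 months".
- Section 9.4: "The study period for reporting serious adverse events will be from the time of signing consent to final study visit".
- Section 9.2 counts a birth defect as a serious adverse event.

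**The concern.** A coordinator who follows section 7 when a subject is stopped for toxicity takes no exit bloods and holds no exit visit. A coordinator who follows 5.2 and 9.3 does both. The two instructions apply to the same person at the same moment, and the protocol does not say which prevails.

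The subjects affected are those for whom closing safety information matters most. Section 10.1 names heart failure symptoms, fluid retention, edema and weight gain as the primary risks, and also mentions dilutional anemia and liver problems. CBC and CMP are the planned laboratory checks for the last two. Section 9.3 wants a resolution date and duration for every event, and both depend on contact after the drug has stopped. The safety monitor described in 13.3, and whoever plans the larger trial, would want to know how the events that ended treatment turned out.

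**Working it through.** The plan states no figure on this point, so the check sets the sections side by side. The only arithmetic concerns timing and a count.

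**1. The sections compared**

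| Moment | Section 7 | Other sections | Compatible? |
|---|---|---|---|
| At stopping | No further activities before withdrawal | 5.2: CBC and CMP at end of treatment | No |
| First visit after drug | None provided for a withdrawn subject | 9.3: adverse events recorded at that visit | No, unless a visit is defined elsewhere |
| Follow-up of an open event | Silent | 9.3: until resolved or stabilized, or 6 months; no exception | Not contradictory, but no mechanism given |
| Serious adverse event window | Silent | 9.4: closes at the final study visit | Undefined for someone dropped early |

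The first two rows are the conflict. The last two are gaps.

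**2. What bloods a dropped subject would have**

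Inputs: dose increase after 2 weeks, or day 14 (8.2); study bloods at baseline, about day 60 and end of treatment (5.2); final on-treatment visit at day 168 ± 14 (13.1).

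- From the dose increase to the next study bloods: 60 − 14 = about 46 days. A subject dropped in that interval for clinical intolerance could leave with baseline CBC and CMP only.
- From the day-60 bloods to the planned end of treatment: 168 − 60 = 108 days, or 182 − 60 = 122 days at the outer edge of the window. A subject dropped on clinical grounds late in treatment could have last study bloods almost that old.

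A subject stopped because of a laboratory abnormality has, by definition, a laboratory result near the time of stopping. For that subject the loss is in what follows, not in the value at exit.

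**3. Pregnancy**

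Section 7 permits withdrawal for pregnancy, and section 9.2 makes a birth defect a serious adverse event. No section says how the study would learn the outcome, so the criterion may never be applied to the subjects it was written for.

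**4. How many subjects**

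The protocol gives no withdrawal rate. Assuming 5% to 25%: 0.05 × 40 = 2 and 0.25 × 40 = 10. Because withdrawn subjects are replaced, more than 40 may be enrolled and the count could be somewhat higher.

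**5. A related mismatch**

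Section 9.3 lists CBC and CMP at baseline and 60 days only, while 5.2 adds the end of treatment. These two need aligning for all subjects.

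**The case against.** The strongest objection is to a broader reading. A reader might infer that section 7 ends all study activity on withdrawal, so that follow-up is nil and the surviving safety data come only from people who tolerated the drug. The documents do not support this:

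- Section 7 speaks of activities before withdrawal. It does not address what comes after, and 9.3 requires follow-up without excepting withdrawn subjects.
- Section 5.8 has side effects reported to the subject's physician, and 10.2 provides for treatment, counseling or referral. Section 9.4 binds the investigator to federal and RSRB reporting rules.
- A subject stopped under the grade II criterion has had the abnormality observed, and 9.3 requires it to be documented with onset, severity, relationship and action taken. The event rate is therefore preserved, and a claim that the profile would look too favourable fails for incidence.
- Section 5.2 frames the main safety issue as whether an adverse effect occurs, not whether it reverses.
- That the 9.4 window closes at the last visit already attended is one reading of an undefined term.

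All of this stands, and it narrows the point. Three further considerations also count. The section 7 sentence may be meant to let people leave without conditions, so any exit assessment must be voluntary. Section 5.2 accepts bloods drawn in routine care, which may fill some of the laboratory gap, though nothing requires such results to be sought for a withdrawn subject. Appendix 1, which holds the visit schedule, is not in the text available and might list an early-termination visit; section 7 would then conflict with it too.

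What the objection does not remove is the clash at the moment of stopping. Nor do notification and referral fill the gap, since they are clinical care and do not oblige anyone to record the outcome for the study.

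**Conclusion.** The point holds in its narrow form. As written, section 7 excludes an exit assessment that 5.2 requires and leaves the post-drug recording in 9.3 without a visit. The protocol also does not say how 9.3 follow-up or the 9.4 window operates after withdrawal. At risk are exit CBC and CMP, the outcome of the event that led to stopping, and later serious adverse events. The occurrence of that event is not at risk.

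The size cannot be derived from the documents. The range of 2 to 10 subjects rests wholly on the assumed 5% to 25% withdrawal rate, and it counts those exposed to the gap, not those whose data would certainly be lost. The conclusion also assumes that Appendix 1 contains no overriding instruction. The point is one of safety reporting and does not bear on the sample size calculation. An amendment is worthwhile because the inconsistency affects subjects stopped for safety and is cheap to remove.

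**What to change.** Reconcile sections 5.2, 7, 9.3 and 9.4 (and Appendix 1, if it covers early termination):

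1. Replace the section 7 sentence with one saying that a subject being withdrawn is asked to complete, if he or she agrees, assessments the protocol already contains: CBC and CMP from 5.2, and the per-visit urinalysis and adverse event questioning from 9.3.
2. State in 9.3 that follow-up of open adverse events continues after withdrawal for the period already given there, by phone or chart review where no visit takes place, with the subject's agreement. Add the end-of-treatment bloods so that 9.3 matches 5.2.
3. Define the final study visit in 9.4 for withdrawn subjects, and say how the 9.2 birth-defect criterion is applied after a pregnancy withdrawal. The pregnancy element is new to the protocol and should be covered in the consent form.

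The rules on who is dropped and when drug is stopped are left unchanged; these edits concern only what is assessed and recorded.

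Cost: a short amendment across these sections, a few extra contacts, and one blood draw per withdrawn subject. Section 5.6 already has the department covering study-specific safety bloods.

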8. STUDY DRUG/DEVICE/BIOLOGIC ADMINISTRATION/ASSIGNMENT

Note: The package insert is included in appendix 2.

8.1. Study Drug/Device/Biologic

Pioglitazone is a currently FDA approved drug. A formal request to conduct the study with the product to obtain an IND is in process. Patients will be provided drug once they consent to participate and are found to be eligible.

8.2. Dosage of Study Drug/Biologic

Subjects will be treated with 15 mg Pioglitazone for the first 2 weeks. If tolerated, the dose will then be increased to 30 mg Pioglitazone daily while on protocol for drug treatment. Subjects unable to tolerate 30 mg Pioglitazone will be dropped from the study.

8.3. Subject Enrollment/Randomization

Subjects will be randomized to one of two study groups: initial observation or initial drug treatment followed by washout.

8.4. Accountability of Investigational Supplies

The study drug is ordered through the investigational drug service. The study drug will be dispensed to the Study Coordinator and transported to the Red Creek clinic site of [name]. It will be stored in a locked cabinet at room temperature until the supply is given to the patient for use. Once patients give consent, the study drug will be dispensed when patients enter the active treatment arm of the protocol. On return appointment, patients will bring their study drug bottle with them. A pill count will be done at each study visit, and the date of drug dispensing will be noted. At the visit prior to completion of the active treatment arm, the exact number of pills required for the planned period until the next study visit will be dispensed to the patient. This will facilitate having patients stop taking drug at the same time as their last “on treatment” study visit.

8.5. Subject Withdrawal of Study Drug

If study subjects stop drug treatment (other than as indicated in the protocol) they will be dropped from the study. Compliance will be considered taking the drug appropriately >80% of the time.

8.6. Emergency Drug Disclosure

Not applicable

9. SAFETY AND REPORTABLE EVENTS

9.1. Adverse Event Definition

An adverse event is any symptom, sign, illness, or experience which develops or worsens during the course of the study, whether or not the event is considered related to study drug.

9.2. Serious Adverse Event

A serious adverse event is defined as any adverse medical experience that results in any of the following outcomes:

- death;
- is life-threatening;
- requires inpatient hospitalization or prolongation of existing hospitalization;
- results in persistent or significant disability/incapacity;
- is a congenital anomaly/birth defect; or
- requires medical or surgical intervention to prevent permanent impairment or damage.

9.3. CBC, CMP will be monitored at baseline and at the study visit occurring 60 days after Drug treatment begins. Urinalysis will be checked for Blood at each study visit.

At each subject visit the study staff will assess adverse events by recording all voluntary complaints of the subject and by assessment of clinical and laboratory features. At each study visit, the subject will be questioned directly regarding the occurrence of any adverse experience since his/her last visit.

All adverse events, whether observed by the Investigator, elicited from or volunteered by the subject, will be documented. Each adverse event will include a brief description of the experience, the date of onset, the date of resolution, the duration and type of experience, the severity, the relationship to taking Pioglitazone, contributing factors, and any action taken with respect to Pioglitazone.

Recording of adverse events will occur during the time that the patient is on study drug and for the next study visit after finishing drug. Follow up of adverse experiences will be until the event is resolved or stabilized or for 6 months.

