13. DATA ANALYSIS AND MONITORING

13.1. Sample Size Determination

[figure not shown]
This pilot study will be designed as a 2-by-2 crossover trial. We refer to Section 2.2 for a justification of the study design. Patients will be enrolled and randomized in one arm of two treatment protocols. Each protocol will include two treatments administered during two consecutive time periods:

- Treatment arm # 1: Patients enrolled in the first arm will first receive six months of usual care (*Period 1*); next, they will be treated with Pioglitazone combined with usual care for the next 6 months (*Period 2*). Patients will take study drug until they come to their final “on Treatment” visit, which will occur 168 days +/- 14 days of their “on Treatment” date.
- Treatment arm # 2: Patients enrolled in the second arm will first receive six months of Pioglitazone treatment combined with usual care (*Period 1*); next, they will receive usual care alone during the following 6 months (*Period 2*). Patients will take study drug until they come to their final “on Treatment” visit, which will occur 168 days +/- 14 days of their “on Treatment” date.

A flow diagram describing the study design is presented in Section 2.

The primary endpoint will be the total number of skin tumors counted during each treatment period. Based on clinical evidence, we expect the total number of skin tumors to range between 0 and 3 per patient and per treatment period (or 0 to 6 per patient per year) and to average around 1.5. We would consider Pioglitazone to be clinically effective if it reduces tumor counts by 50% (that is, reduce the average number of tumors from 1.5 to 0.75 per patient and per treatment period). Previous work by this investigator has shown that such reductions in tumor numbers can occur when prostaglandin metabolism is affected by drug treatment (Elmets *et al.*, 2010).

A two-sided *t*-test achieves 96% power to detect a reduction in the number of skin tumors due to Pioglitazone when the total sample size of a 2-by-2 crossover design is 40 (20 patients per group). The calculations assumed that the actual mean difference is 0.75 (corresponding to a 50% reduction in the mean number of skin tumors due to treatment), the square root of the within mean square error is 1, and the significance level is 5%. The figure below displays the power of the study as a function of the sample size (N) for three values of the square root of the within mean square error (SW).

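### One sentence in Section 9.3 limits adverse-event recording to time on drug plus one visit, in conflict with 9.1 and the rest of 9.3, and would leave arm 1's usual-care period without non-serious event data

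*Combined protocol and SAP*

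**What the plan says.** The recording rule is the closing paragraph of the text numbered 9.3, printed after the list of seriousness criteria in 9.2: "Recording of adverse events will occur during the time that the patient is on study drug and for the next study visit after finishing drug".

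Three other statements in Section 9 are wider:

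- Section 9.1 defines an adverse event as one "which develops or worsens during the course of the study, whether or not the event is considered related to study drug".
- Section 9.3, on elicitation: "At each study visit, the subject will be questioned directly regarding the occurrence of any adverse experience since his/her last visit".
- Section 9.3, on documentation: "All adverse events, whether observed by the Investigator, elicited from or volunteered by the subject, will be documented".

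Serious events have their own window in Section 9.4: "The study period for reporting serious adverse events will be from the time of signing consent to final study visit".

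Section 8.3 randomises subjects to "initial observation or initial drug treatment followed by washout". Section 13.1 gives the periods. For arm 1, "Patients enrolled in the first arm will first receive six months of usual care" before any drug. For arm 2, after the drug period, "they will receive usual care alone during the following 6 months".

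**The concern.** A coordinator who hears of new ankle swelling at an arm 1 usual-care visit must document it under one sentence of 9.3 and has no instruction to record it under another. Different staff could resolve this differently, and off-drug data collected that way could not be interpreted.

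If the narrow sentence governs, the loss falls on the events that matter most for this drug. Section 5.2 lists weight, pedal edema, dyspnea, headache and myalgia among the safety endpoints. Section 10.1 puts fluid retention, edema and weight gain among the main risks, with headache, muscle pain and respiratory infection as minor ones. Many such events would not meet the seriousness criteria of 9.2, so the wider window in 9.4 does not capture them. Sections 3.1 and 5.2 describe a mostly older population with co-morbidities, in whom these complaints can be expected without the drug.

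The trial is open label, and 9.3 asks for a judgement of relationship to pioglitazone for each event. An off-drug rate gathered in the same way would be a useful check on those judgements. It would also be useful to the larger study that this pilot is meant to inform (Sections 1.1 and 2.1).

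**Working it through.** The plan states no figure on this point, so there is none to reproduce. The check sets the texts side by side and then counts person-time.

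**Step 1: the texts.**

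| Source | Window or scope | Covers arm 1 usual care? | Covers arm 2 usual care? |
|---|---|---|---|
| 9.1, definition | Whole study, any cause | Yes | Yes |
| 9.3, questioning | Every study visit | Yes | Yes |
| 9.3, documentation | All adverse events | Yes | Yes |
| 9.3, closing paragraph | On drug plus next visit | No | To the next visit only |
| 9.4, serious events | Consent to final visit | Yes | Yes |

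The fourth row conflicts with the first three. The fifth is a wider rule for a subset of events and can be followed alongside the fourth.

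**Step 2: inputs for person-time.** There are 40 subjects, 20 per arm, and two periods of six months (Section 13.1). No dropout is assumed. The visit schedule is in Appendix 1, which is not shown, so the time from the end of drug to the next visit, m months, is an assumption varied from 1 to 6.

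**Step 3: planned person-months.**

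- On drug: 40 x 6 = 240.
- Usual care, arm 1, Period 1: 20 x 6 = 120.
- Usual care, arm 2, Period 2: 20 x 6 = 120.
- Total usual care: 120 + 120 = 240.

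**Step 4: usual-care time covered for non-serious events under the narrow sentence.** Arm 1 contributes 0 of 120. Arm 2 contributes 20 x m, on the generous reading that the next visit captures everything since the previous one.

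| m (assumed) | Covered (20 x m) | Share of 240 covered | Unrecorded (240 - 20 x m) | Share unrecorded |
|---|---|---|---|---|
| 1 | 20 | 8% | 220 | 92% |
| 2 | 40 | 17% | 200 | 83% |
| 3 | 60 | 25% | 180 | 75% |
| 6 | 120 | 50% | 120 | 50% |

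For serious events, coverage under 9.4 is 240 of 240.

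**Step 5: what kind of time is lost.** Arm 1's Period 1 is the only usual-care time that precedes all drug exposure and runs alongside randomised drug treatment (arm 2, Period 1). Any covered time in arm 2 comes after exposure, and Section 8.3 calls it washout. The 120 person-months in arm 1 are unrecorded whatever value m takes.

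**The case against.** Several points on the other side stand.

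- **Which sentence governs is not settled.** If the each-visit and all-events sentences prevail in practice, off-drug events are collected and nothing is lost. The conflict in the text is certain; the loss of data is conditional.
- **No adverse-event comparison is planned.** The purposes in 1.1 concern tumor counts, recurrence, phenotype and markers. Section 13.2 contains no safety contrast, and 5.2 uses safety data for screening and stopping. A comparison rate is a reasonable addition, not something the plan promises and fails to deliver. Even so, events that were never recorded cannot be recovered later.
- **Misattribution is limited.** Section 9.3 requires an onset date and contributing factors for each event, so an event that began before drug should carry a pre-drug date.

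A reader might also infer four stronger claims, which the documents do not support:

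- *Usual-care time yields no adverse-event rate at all.* Serious events are recorded throughout under 9.4, and arm 2 is covered to the next visit.
- *Section 9.4 contradicts 9.3.* Separate windows for serious and other events can both be followed.
- *Nearly all off-drug time goes unrecorded.* That depends on a schedule not shown; the unrecorded share is 50% if the next visit is at six months.
- *Full recording would give a within-subject excess rate from 40 complete pairs.* Sections 5.2, 7 and 8.5 drop subjects for grade II abnormalities, intolerance or stopping drug, and Section 7 replaces withdrawn subjects. An arm 2 subject dropped on drug has no usual-care period to pair, so the subjects of most interest would be the ones missing.

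**Conclusion.** The concern holds in a limited form. The closing paragraph of 9.3 is inconsistent with 9.1 and with the rest of 9.3, and the texts must be reconciled. Followed as written, the closing paragraph leaves non-serious events unrecorded in all 120 person-months of arm 1's initial usual care, half of the 240 planned off-drug person-months. It also leaves them unrecorded in arm 2's usual care after the next visit. The trial would then have no drug-naive, concurrent comparison rate for the non-serious events that it names as safety concerns.

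The 120 rests on 20 subjects per arm, full six-month periods and no dropout, and on the narrow sentence being the one applied. The arm 2 loss cannot be fixed without the visit schedule. Serious-event data and the planned tumor analysis are unaffected. This is a change that should be made; it does not undermine the trial's primary aim.

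**What to change.** Replace the recording sentence in 9.3 with wording to this effect: *all adverse events, serious or not, are recorded from signing of consent to the final study visit, in both arms and both periods*. This agrees with 9.1 and with the questioning and documentation sentences of 9.3, and uses the window that 9.4 already sets for serious events.

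Add a line to 13.2 for a descriptive table of adverse events per person-time on drug and on usual care, by arm and period, using the person-time actually observed. State beside the table that subjects dropped for toxicity contribute incomplete pairs and that arm 2's usual-care time follows exposure. The Period 1 contrast between arms needs no pairing and should be shown separately.

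The cost is some extra log entries and one descriptive table. Section 9.3 already requires subjects to be questioned at every study visit, so the change adds no new questioning.
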